### **Surgery**

Major surgery (e.g., surgical procedure involving an organ within the cranium, chest, abdomen, or pelvic cavity) or major procedures in tissue with high fibrinolytic activity (e.g., gynecologic, urologic, or surgeries of the nasal and oral cavities) or surgeries with high risk for perioperative bleeding, should not be performed during the trial. However, if deemed medically necessary and surgery cannot be postponed until the end of the follow-up period, the surgery is only allowed to be performed under general anesthesia. Spinal or epidural anesthesia/analgesia is not allowed during the study. Investigators are encouraged to postpone surgeries whenever possible until the end of the study including the 4 months follow-up period or at least as long as possible after the last study intervention. Hence, study intervention should be immediately discontinued if a participant is scheduled for the above mentioned surgeries. Participants who permanently discontinue study intervention due to a surgery will enter the post-treatment follow-up period (Section 7.1).

Minor surgeries or surgeries with low bleeding potential (e.g., knee replacement surgery) may be performed during the trial if deemed necessary and can't be postponed. Of note, during the FOXTROT trial participants have been operated for total knee replacement under full anti-coagulation with osocimab (doses up to 1.8 mg/kg). Study interventions may be further administered after such surgery if deemed appropriate by the investigator and after careful post-operative assessment. Before restarting study intervention administration of prohibited concomitant medication needs to be taken into account (Section 6.5).

If knowledge of treatment assignment will influence the choice of intervention to manage bleeding risk prior to or during the surgery the investigator may immediately obtain the participant's treatment assignment by contacting IWRS. In this setting, it is appropriate to monitor coagulation parameters.

Management of bleeding and surgery of study participants may further be guided by published data regarding patients with inherited FXI deficiency. There have been reports in the literature about the successful use of tranexamic acid or  $\epsilon$ -amino caproic acid in the management of non-ESRD, hemophilia C patients when undergoing surgery (26). The local package insert need to be consulted for usage in patients with ESRD on dialysis. In patients

undergoing tooth extractions, i.e. an invasive procedure in tissue with high fibrinolytic activity in the oropharynx, Berliner et al. reported uneventful extractions in 19 patients with severe FXI deficiency treated with tranexamic acid alone (1 g q.i.d.) started 12 h prior to surgery and continued for 7 days after surgery (27). The administration of recombinant FVIIa in addition to tranexamic acid was also reported as a therapeutic option in patients with severe FXI deficiency undergoing surgery (28- 29). O'Connell et al. reported effective hemostasis when a dose of 90  $\mu$  g/kg of recombinant FVIIa given every two hours in the first 24 hours and every 4 hours in the second 24 hours, followed by postoperative tranexamic acid for 7 days, was used in patients undergoing major surgery. Subsequently, Livnat et al. showed that even a single dose of recombinant FVIIa at a dose of 15-30  $\mu$  g/kg, along with 1 g of tranexamic acid given before surgery and then every 6 hours post-surgery for 7-14 days achieved satisfactory hemostasis in patients with FXI inhibitors undergoing major surgery (30).

Please consider that for severe renal impairment/ESRD specific limitation or even contraindications for use of certain agents may apply. This may differ between countries.

### 8.2.3 Physical Examinations

A complete physical examination will include, at a minimum, assessments of the cardiovascular, respiratory, gastrointestinal and neurological systems and will follow standard practice of the site. Height will only be measured at screening visit. Weight will be measured pre- and post-hemodialysis (dry-weight).

### 8.2.4 Vital Signs

- Vital signs will consist of 1 pulse and 1 blood pressure measurements. Vital signs will be measured after 5 minutes rest.
- Blood pressure and pulse measurements will be assessed pre-dialysis (with the exception of the screening visit), either in a supine or sitting position (preferably in the same position for all visits), on the same arm at each visit, and using the appropriate size cuff. These measurements will be performed at the time points specified in the SoA (see Section 1.3).

NOTE: The AV graft or fistula arm cannot be used to measure blood pressure.

### 8.2.5 Electrocardiograms

- Single standard electrocardiograms (12 lead ECG) according to Goldberger / Einthoven and Wilson will be recorded pre-dialysis after resting for at least 5 min at the time points specified in the SoA (see Section 1.3).
- All ECG print-outs will be identified with the PID as well as date and time of recording and will be attached to the participant's file.
- ECG printouts will be examined locally by the investigator on the day of recording for safety and quality. Any clinically relevant abnormality will be documented as an AE.
- All suspected acute coronary syndrome events need to be submitted to the CIAC for evaluation.

## 8.2.6 Clinical Safety Laboratory Assessments

- See Section 10.2 for the list of clinical laboratory tests to be performed and the SoA (Section 1.3) for timing and frequency.
- The investigator must review the laboratory report, document this review, and record any clinically relevant changes occurring during the study in the AE section of the eCRF. The laboratory reports must be filed with the source documents. Clinically significant abnormal laboratory findings are those which are not associated with the underlying disease, unless judged by the investigator to be more severe than expected for the participant's condition.
- All laboratory tests with values considered clinically significantly abnormal during participation in the study or until the end of study should be repeated until the values return to normal or baseline or are no longer considered clinically significant by the investigator or the medical monitor.
  - If such values do not return to normal/baseline within a period of time judged reasonable by the investigator, the etiology should be identified and the sponsor notified.
  - All protocol-required laboratory assessments, as defined in Section 10.2, must be conducted in accordance with the laboratory manual and the SoA.
  - If laboratory values from non-protocol specified laboratory assessments performed at the institution's local laboratory require a change in participant management or are considered clinically significant by the investigator (e.g., SAE or AE or dose modification), then the results must be recorded in the eCRF.
- Appropriate blood draws from the dialysis access for any type of blood sampling, collected from the hemodialysis line (not directly from the fistula, nor from any vein on the fistula arm), or tunneled catheters are permitted. Whenever possible, the blood should be drawn under the same conditions (details are depicted in the laboratory manual).
- Where possible for safety laboratory, pediatric-sized blood volumes (as opposed to adult-sized blood volumes) are to be taken and blood collections should be combined to minimize the number of needle punctures.
- During the screening visit, only local laboratory samples will be assessed to check the eligibility of the patient. For details see Section 10.2.

Central lab results for PD parameters including coagulation parameters will not be provided to the sites, as these are potentially unblinding. Investigators should also avoid local testing of coagulation parameters, as these may be unblinding, unless clinically indicated.

## 8.2.7 Dialysis Information

### 8.2.7.1 Renal Replacement Therapy (RRT) Baseline Information (General Dialysis Information)

Current dialysis prescription will be collected on the appropriate eCRF.

Note: anticoagulation use during hemodialysis must be reported in the Concomitant Medication page in the eCRF.

### **8.2.7.2 Dialysis Prescription Changes**

Changes to the dialysis prescription and compliance with dialysis will be recorded on the appropriate eCRF at visits specified in the SoA.

Note: changes in anticoagulation use during hemodialysis must be reported on the appropriate eCRF page.

## **8.3 Adverse Events and Serious Adverse Events**

AEs will be reported by the participant (or, when appropriate, by a caregiver, surrogate, or the participant's legally authorized representative).

The investigator and any qualified designees are responsible for detecting, documenting, and recording events that meet the definition of an AE or SAE and remain responsible for following up AEs that are serious, considered related to the study intervention or study procedures, or that caused the participant to discontinue the study intervention or study (see Section 7).

### **8.3.1 Time Period and Frequency for Collecting AE and SAE Information**

All AEs/SAEs will be collected from signing of informed consent until the last follow-up visit at the time points specified in the SoA (Section 1.3).

All SAEs will be recorded and reported to the sponsor or designee immediately and under no circumstance should this exceed 24 hours, as indicated in Section 10.3. The investigator will submit any updated SAE data to the sponsor within 24 hours of it being available.

Investigators are not obligated to actively seek AE or SAE after conclusion of the study participation. However, if the investigator learns of any SAE, including a death, at any time after a participant has been discharged from the study, and he/she considers the event to be reasonably related to the study intervention or study participation, the investigator must promptly notify the sponsor.

### **8.3.2 Method of Detecting AEs and SAEs**

The method of recording, evaluating, and assessing causality of AE and SAE and the procedures for completing and transmitting SAE reports are provided in Section 10.3.

Care will be taken not to introduce bias when detecting AEs and/or SAEs. Open-ended and non-leading verbal questioning of the participant is the preferred method to inquire about AE occurrences.

### **8.3.3 Follow-up of AEs and SAEs**

After the initial AE/SAE report, the investigator is required to proactively follow each participant at subsequent visits/contacts. All SAEs, and AESIs (as defined in Section 8.3.8), will be followed until resolution, stabilization, the event is otherwise explained, or the participant is lost to follow-up (as defined in Section 7.3). Further information on follow-up procedures is provided in Section 10.3.

### **8.3.4 Regulatory Reporting Requirements for SAEs**

- Prompt notification by the investigator to the sponsor of an SAE is essential so that legal obligations and ethical responsibilities towards the safety of participants and the safety of a study intervention under clinical investigation are met.

- The sponsor has a legal responsibility to notify both the local regulatory authority and other regulatory agencies about the safety of a study intervention under clinical investigation. The sponsor will comply with country-specific regulatory requirements relating to safety reporting to the regulatory authority, Institutional Review Boards (IRB)/Independent Ethics Committees (IEC), and investigators.
- For all studies except those utilizing medical devices investigator safety reports must be prepared for suspected unexpected serious adverse reactions (SUSAR) according to local regulatory requirements and sponsor policy and forwarded to investigators as necessary.
- An investigator who receives an investigator safety report describing an SAE or other specific safety information (e.g., summary or listing of SAEs) from the sponsor will review and then file it along with the Investigator's Brochure and will notify the IRB/IEC, if appropriate according to local requirements.

### Reporting of Disease-Related Events

Overall, in compliance with applicable regulations, in the event of a SUSAR related to the blinded treatment, the participant's treatment code will usually be unblinded before reporting to the health authorities. Notifications of IEC/IRB and investigators will be done according to all applicable regulations (see Section 8.3.4) with the restrictions described below.

During the study there will be instances where AEs are also potential efficacy or safety endpoints.

The following efficacy and pre-defined disease-related outcome events are expected in patients with ESRD

- i. Bleeding
- ii. Death due to MI, stroke, PE and SE
- iii. Non-fatal stroke
- iv. Non-fatal MI
- v. Major amputation of vascular etiology
- vi. Acute limb ischemia
- vii. Symptomatic VTE
- viii. Thrombosis of AV fistulas or grafts

These will be recorded on the corresponding CRF page in the participant's eCRF.

If any of the above listed outcome events fulfil the definition of SAEs as given in Section 10.3, the investigator must report them immediately (within 24 hours of the investigator's awareness) to the sponsor's pharmacovigilance department as described in Section 10.3. However, SUSARs that derive from these efficacy outcome events (as specified above ii – viii: Death due to MI, stroke, PE and SE, non-fatal stroke, non-fatal MI, major amputation of vascular etiology, acute limb ischemia, symptomatic VTE, thrombosis of AV fistulas or grafts), including events indicative of those outcome events (details will be described in the adjudication charter and additional study specific guidance documents) will be waived from unblinding and are not subject to expedited reporting to health authorities. In case of unblinding, SUSARs may be submitted blinded, either expedited or aggregated, to

investigators and IEC/IRB. Unblinded SUSAR reports are submitted only when required by local legislation.

### **8.3.5 Pregnancy**

- Details of all pregnancies in female participants and, if indicated, female partners of male participants will be collected after signing of informed consent and until the last follow-up visit (visit 35).
- If a pregnancy is reported, the investigator should inform the sponsor within 24 hours of learning of the pregnancy and should follow the procedures outlined in Section 10.4.
- Abnormal pregnancy outcomes (e.g., spontaneous abortion, fetal death, stillbirth, congenital anomalies, ectopic pregnancy) are considered SAEs.
- As serum beta human chorionic gonadotropin ( $\beta$ hCG) levels are high in pregnant and may be elevated in non-pregnant women with ESRD undergoing hemodialysis, one measurement of high  $\beta$ hCG may not be sufficient to establish pregnancy. Only sequential increasing levels of  $\beta$ hCG may be considered for further investigation on pregnancy. If deemed necessary, a follow-up ultrasound may be performed to confirm pregnancy. If a female participant becomes pregnant, she must permanently discontinue study intervention.

### **8.3.6 Cardiovascular and Death Events**

Not applicable.

### **8.3.7 Disease-Related Events and/or Disease-Related Outcomes Not Qualifying as AEs or SAEs**

Bleeding after dialysis from AV graft or fistulas is expected and will only be reported as an AE or SAE if there is a change in the pattern or intensity of bleeding in a participant, or if exceptional measures are taken for hemostasis beyond normal, relative to post-dialysis bleeding that was observed in that participant over the prior 4 weeks.

### **8.3.8 Adverse Events of Special Interest**

Adverse events of special interest have to be reported to the sponsor along the timelines set for SAEs, i.e. within 24 hours of the investigator's awareness, as described in Section 8.3.1.

Declaration of an event as serious should only occur if one or more of the serious criteria is applicable. Non-serious adverse events of special interest should not automatically be upgraded to serious by the reporting investigator.

Adverse events of special interest are:

- Decrease in platelets below  $75 \times 10^9/L$  or  $> 50\%$  decrease in platelet count from baseline
- Hypersensitivity (i.e. any allergic reactions of  $\geq$  CTCAE criteria 2 [Common Terminology Criteria for Adverse Events] or anaphylaxis)

### **8.3.8.1 Stopping Rule for Study Drug Administration in Case of Thrombocytopenia**

In the event of a platelet count that is  $< 75,000\text{mm}^3$ , or  $> 50\%$  decrease in platelet count from baseline the initial measurement should be confirmed by drawing repeat measurement(s) within 2 weeks. The repeat measurement(s) must occur before further study intervention (i.e. study drug administration). In the event that the platelet count has not recovered to  $> 100,000\text{ mm}^3$  within 2 weeks, dosing of the participant will be postponed until the platelet has increased at least above  $100,000\text{ mm}^3$ . In the event that after resumed dosing thrombocytopenia ( $< 75,000\text{ mm}^3$ ) occurs again, study drug administration will be stopped permanently. A participant may be withdrawn from study intervention at any time at the discretion of the investigator for safety reasons (Section 7.1).

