**Table 1–2: Schedule of Activities – Extension Treatment Period and Follow-up Period**

Study period (Duration)	Extension treatment period (up to 12 months)													Follow-up period (For 4 months after EOMT or EOET)				Notes
Visit number	19 b	20	21	22	23	24	25	26	27	28	29	30	31/EOET ED a	32	33	34	35	
Study intervention MD	MD	MD	MD	MD	MD	MD	MD	MD	MD	MD	MD	MD						
Day since last study intervention dose	30	30	30	30	30	30	30	30	30	30	30	30	30	60	90	120	150	
Approx. month	7	8	9	10	11	12	13	14	15	16	17	18	19	20	21	22	23	
Window (days)	± 3	± 3	± 3	± 3	± 3	± 3	± 3	± 3	± 3	± 3	± 3	± 3	± 3	± 5	± 5	± 5	± 5	A deviation of 2-3 days equals 1 dialysis session. Section 7.1.
Study intervention																		
Study intervention administered	•	•	•	•	•	•	•	•	•	•	•	•						Administered sc abdominally within one hour prior to dialysis.
Laboratory Assessment																		
Central laboratory	Laboratory calculated URR and Kt/V			•				•					•					For BUN a post-dialysis sample needs to be taken (central lab). Local lab values of URR and Kt/V ± 7 days are accepted.
	Hematology, chemistry, coagulation and serum pregnancy			•				•					•				•	Pre-dialysis. Prior to study intervention.
	Biomarkers d								• c				• c					Pre-dialysis. Prior to study intervention.
	Main PD d samples								• c				• c	• e	•	• e	•	
	PK samples								• c				• c	• e	•	• e	•	
ADA/NAB								• c				• c	• e	•	• e	•		

Abbreviations: ADA = anti-drug antibodies, AE = adverse event, AESI = adverse event of special interest, Approx. = approximately, AV = arteriovenous, BUN = blood urea nitrogen, ECG = electrocardiogram, ED = early discontinuation visit, EOET = end of extension treatment period visit, EOMT = end of main treatment period visit, IWRS = interactive web response system, Kt/V – K = dialyzer urea clearance, t = dialysis time, V = total volume of distribution of urea, MD = maintenance/ monthly dose,

NAB = neutralizing antibodies, PD = pharmacodynamic, PK = pharmacokinetic, sc = subcutaneous, SQCS = semi-quantitative clotting score, URR = urea reduction ratio

- a. It is recommended to perform the ED visit approximately 1 month after last study intervention. After ED the participant moves directly to the follow-up period.

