- b. EOMT and visit 19 will be at the same day. Both of them are mandatory separate visits and shouldn't be missed.
- c. Samples are taken prior to study intervention at visit 27 or EOET/ED, whichever comes first.
- d. Study participating sites in China are excluded from all PD and biomarker sampling and analyses.
- e. Samples need to be taken only if no sampling was done approximately 30 days before at a prior visit.

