### 7.1.1 Temporary Discontinuation

This protocol does not allow any pre-planned alteration from the currently outlined dosing schedule. However, there may be rare circumstances due to which the investigator may need to temporarily discontinue study intervention for an adverse event (Section 8.3), bleeding event (Section 8.2.2), or surgery (Section 8.2.2.2) and any other reason not listed as reasons for discontinuation of study intervention (Section 7.1) or withdrawal from the study (Section 7.2).

The following guidance should be observed in case maintenance dosing cannot be administered according to dosing schedule.

Delayed maintenance dosing:

A dose is delayed if it is given up to 4-7 days from the original schedule. The dose should be administered at the next possible time point, but not later than 7 days than originally scheduled.

Missed maintenance dosing:

Any dose which is delayed for more than 7 days will be considered as missed dose. The dose should be administered at the next possible time point, but not later than 60 (+3) days after the last given dose. There should be also minimum 30 days  $\pm$  3 days between the doses. If the dose is delayed more than 60 (+3) days after the last given dose, the participant will need to move into the follow-up period. Only one maintenance dose can be missed (i.e. given > 7 days after the originally scheduled dosing and not later than 60 (+3) days after the last actually administered dose) per main treatment or per extension treatment period. Between missed doses at least 5 regular maintenance doses should have been administered according to protocol, otherwise the participant will also need to move into the follow-up period. Obtain blood samples for PK/PD analysis 30 ( $\pm$ 3) days after the date of the delayed dose, if not already scheduled according to the study protocol.

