## **10.2 Appendix 2: Clinical Laboratory Tests**

For details on the sampling scheme, please refer to Section 1.3 Schedule of Activities (SoA).

- The tests detailed in [Table 10–1](#) will be mostly performed by the central laboratory.
- Central laboratory results may not be available in time for necessary medical decisions. Therefore, local laboratory tests are performed according to usual patient care schemes at the site, per decision of the investigator/treating physicians. If SAEs are triggered by local laboratory results the respective findings must be documented in the eCRF.
- Protocol-specific requirements for inclusion or exclusion of participants are detailed in Section 5 of the protocol.

- Additional tests may be performed at any time during the study as determined necessary by the investigator or required by local regulations.
- Pregnancy Testing
- Biomarkers (for details see Section 8.8)

Pharmacodynamic and pharmacokinetic parameters as well as safety laboratory parameters will be analyzed by central laboratories. The names and the addresses of the central laboratory service providers can be found in the documentation supplied by the vendor (laboratory manual).

During the screening visit, only local laboratory samples will be assessed to check the eligibility of the patient.

At least all parameters listed in [Table 10–1](#) under screening tests at local laboratory must be assessed at the screening visit and entered in the eCRF to check the patient's eligibility for the study.

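### After a platelet event recovers above 100,000, Protocol 8.3.8.1 requires no count before later doses, and 9 of 12 extension doses have no scheduled count

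*Protocol*

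**What the plan says.** Protocol 8.3.8.1 is triggered by a count below 75,000/mm³ or a fall of more than half from baseline. It asks for a repeat within two weeks and before any further dose. If the count is not back above 100,000 by then, dosing waits until it is. The last step begins "In the event that after resumed dosing thrombocytopenia" and provides that, if a count below 75,000 "occurs again, study drug administration will be stopped permanently". The section sets no count before doses that follow recovery.

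Scheduled platelet counts come from the central hematology panel. In Table 1–1 (main period) the panel is drawn about once per dose. In Table 1–2 the row "Hematology, chemistry, coagulation and serum pregnancy" carries only four marks across the extension and follow-up.

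Other sections that bear on the point:
- 8.2.6: clinically significant abnormal values "should be repeated until the values return to normal or baseline or are no longer considered clinically significant by the investigator" or the medical monitor.
- 8.3.3: events of special interest "will be followed until resolution, stabilization, the event is otherwise explained", or the participant is lost to follow-up.
- 10.2: "local laboratory tests are performed according to usual patient care schemes at the site", as the investigator or treating physician decides. The same section warns that central results can come too late for medical decisions.
- 7.1.1: limits missed doses. For sampling after an off-schedule dose it says "Obtain blood samples for PK/PD analysis 30" (±3) days later, with no mention of platelets.

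**The concern.** A stopping rule keyed to a laboratory value can act only if the value is measured. Table 2–1 lists thrombocytopenia as a potential risk and names regular safety laboratory tests and this stopping rule among its mitigations. In the extension the schedule thins out for everyone, including a participant with a known platelet event. Such a participant could be re-dosed while a second fall goes unmeasured. Section 2.2.4 gives a terminal half-life of about 30 to 44 days (after intravenous dosing), so a dose given during an unnoticed recurrence cannot be quickly undone. Heparin for dialysis and low-dose ASA are both permitted alongside.

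**Working it through.** **Step 1: place the hematology marks.** The columns of Table 1–2 are broken in the text copy, and the hematology row is one cell short. Its marks are at cells 3, 7, 12 and 16. The biomarker row, equally short, has marks at cells 8 and 12. Footnote c fixes those: "Samples are taken prior to study intervention at visit 27 or EOET/ED, whichever comes first". So cell 8 is V27 and cell 12 is V31/EOET, and cell p is visit 19 + p. Hematology is therefore at V22, V26, V31/EOET and V35.

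**Step 2: count the doses.** Doses are given at V19 to V30, which is 12. V19 falls on the same day as EOMT, which includes hematology, so V19 is credited. Doses with a scheduled count: V19, V22, V26 = 3. Without: 12 − 3 = 9 (V20, V21, V23–V25, V27–V30). Other readings of the row give 8 to 10; 9 is best supported. Nominal gaps between scheduled counts are 3 × 30 = 90, 4 × 30 = 120 and 5 × 30 = 150 days.

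**Step 3: count the uncovered doses after an event.** A dose is uncovered if neither 8.3.8.1 nor the schedule requires a count for it.

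| Event found at | No dose held: repeat covers | Uncovered | One dose missed, then resumed at | Uncovered |
|---|---|---|---|---|
| EOMT/V19 | V20 | V21 = 1 | V21 | none = 0 (V22 is scheduled) |
| V22 | V23 | V24, V25 = 2 | V24 | V25 = 1 |
| V26 | V27 | V28, V29, V30 = 3 | V28 | V29, V30 = 2 |

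The resumed dose counts as covered because recovery above 100,000 must be shown first. A short delay within the 7 days that 7.1.1 allows drops no visit and is not tabulated separately. A shorter extension gives fewer uncovered doses, since EOET includes hematology.

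**Step 4: match the clause to the case.** The permanent-stop clause concerns resumed dosing, so it belongs to the right-hand columns (0, 1, 2). In the left-hand columns (1, 2, 3) a new fall would trigger the ordinary confirm-and-hold rule, and it is that rule which has no count to act on.

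**Step 5: test the backstops.** Repeats under 8.2.6 can end at normal, at baseline, or when judged not significant. Follow-up under 8.3.3 can end at stabilization. Local tests under 10.2 have no stated frequency. Reporting within 24 hours runs from awareness of an event, and the DMC sees only results that exist. The 7.1.1 limits act on doses already missed. None of these requires a count before an uncovered dose.

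**The case against.** The strongest defense is that this is a proportionate design. Counts are thinned only after six months of roughly per-dose hematology. The documents report no observed thrombocytopenia signal; the rationale in Table 2–1 cites only FXI activity and aPTT. Participants attend dialysis about three times a week, where local tests are part of usual care, and the investigator may test or withdraw at any time. Crossing 100,000 does not by itself end repeats under 8.2.6. Section 7.1.1 allows one missed dose per period, asks for at least five regular doses between missed ones, and moves anyone more than 60 (+3) days from the last dose to follow-up. Prolonged or repeated holds therefore end dosing anyway.

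Much of this stands. It confines the gap mainly to recurrence after an event judged resolved or stable, in few people. It does not close the gap, because a site can follow every section as written and give the uncovered doses without a count.

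A reader might infer that the permanent-stop clause can be bypassed for three doses. The documents do not support that: three arises only when no dose was held, where that clause is not engaged. After one missed dose the most is two. Nor do they support the inference that platelet follow-up ceases after an event, since 8.2.6, 8.3.3 and 10.2 all provide some.

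**Conclusion.** The gap is real and small. After recovery above 100,000, 8.3.8.1 ties no count to later doses. In a full extension 9 of 12 doses have no scheduled count, and uncovered doses after an event number 1, 2 or 3 (no hold) or 0, 1 or 2 (one missed dose, then resumed). Even the scheduled counts do not clearly gate the dose, since they are central samples drawn on the dosing day.

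The figures assume the full 12 months, the column reading in step 1, nominal 30-day visits, and credit for the EOMT sample at V19.

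A reader might also infer damage to the primary result. The primary analysis uses only the main treatment period (Protocol 9.4.1), where counts are about one per dose, so it is unaffected. This is a cheap safety improvement that should be made; it is no threat to the trial's conclusions.

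**What to change.** Add to 8.3.8.1, with a matching footnote in Table 1–2: after a confirmed platelet event or a platelet hold, a local platelet count from a dialysis session shortly before each further extension dose must be reviewed before that dose is given, for the rest of treatment. Keep the 75,000 and 100,000 thresholds.

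The requirement should run to the last dose. Ending it after two satisfactory counts would cover V27 and V28 after a V26 event but leave V29 and V30 open.

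The cost is one small local sample per extension dose, in affected participants only. That is up to 11 for an event found at EOMT/V19 (V20–V30) and up to 12 for an earlier one (V19–V30). If main-period doses were included, an event at V8 would need up to 4 + 12 = 16 (V11, V13, V15, V17, then V19–V30). The documents give no platelet-event rate. Assuming 1% to 5% of the 555 expected main-period completers, 6 to 28 people would be affected (555 × 0.01 = 5.55; 555 × 0.05 = 27.75), or at most 6 × 12 = 72 to 28 × 12 = 336 samples.

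The drug is given within the hour before dialysis, so the sample will usually come from the preceding session. That session may be outside the study center, so the result must be sent to the investigator. SAP 6.4.7 analyzes only central samples, so the planned laboratory tables do not change.
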